2.1. Potential impact of the proposed research

Should this trial be successful, we will have a scalable solution for breaking the unfortunate cycle of reoccurrence of depression among adolescents, which will have long-term beneficial impact. Based on prediction analysis, the two different alternatives of relapse prevention in this trial, including either clinician supported intervention or self-help intervention, allow for staging of care according to individual needs and cost-benefit calculations.

Anxiety and depression often go hand in hand with physical complaints. The “Tankevirus”-program targets transdiagnostic factors underlying physical complaints and pain and might therefore be beneficial in a broader health related context and reduce the overall burden associated with recurrent depression in adolescence on the health care system.

This trial will in addition to depression relapse, also investigate the diagnostic instability represented by the cross over from anxiety to depression. In this undescribed field of research, this represents a major leap when quantifying the potential benefit of introducing programs in an intermittent phase of the disorders and hinder its transgression into episodes of depression. Hence, this high-quality large-scale trial with long-term follow-up will provide evidence for the efficacy of depression relapse interventions among adolescents. The head-to-head comparison of interventions will disentangle the level of clinician-involvement required, and the inclusion of a cost-effectiveness analysis will bring leverage for its implementation.

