1.2. Novelty and ambition

A main objective of this this multiarmed trial is to compare two digital versions of a transdiagnostic prevention program with varying level of therapist guidance, to assessment-only. The “Tankevirus”- (eng.: Thought viruses) program offers easily accessible, popularized knowledge and advice on how to develop psychological resilience. It is based on the principles of CBT and makes available different strategies for targeting heuristics and thinking traps leading to rumination and worry. By reducing thought viruses, risk of relapse can be reduced.

Digital interventions targeting mental health problems has grown profoundly more popular due to its availability, accessibility, scalability, and low cost associated with its use. Importantly, clinical trials investigating their effectiveness suggests that they offer value for money when compared with no intervention and non-therapeutic controls, but maybe not when controlled to interventions led by therapists (27). However, a direct comparison between digital interventions and therapist-led interventions in relation to relapse has not been conducted and no digital interventions for relapse prevention has been investigated in adolescent populations.

By investigating the efficacy of two types of digital interventions with different need for therapist involvement, and predictors for their effect, this trial will offer new insights and strategies for reducing relapse among adolescents, potentially paving the way for relapse prevention in the format of a readily accessible, personalized, digital solution for adolescents that can be easily implemented nationwide. By assessing the cost-effectiveness of the different versions of the interventions we can identify whether therapist involvement is necessary. While previous relapse prevention trials have shown efficacy (18), they have not been health economically evaluated. Digital intervention has an obvious economical advantage compared to individualized, therapist-guided interventions, however, the evidence regarding the cost-effectiveness of digital tools is scattered (28).

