INTERVENTIONS: “Tankevirus” is an award-winning psychological intervention developed for adolescents aged 16 and above, including a book, a mastery course, and a smartphone app. It is based on the principles of CBT to help individuals identify and challenge negative thought patterns that can lead to anxiety and depression. “Tankevirus” has been extensively evaluated. From 2017-2021, 50.000 students took part in the overarching “Tankevirus” School program, and 9 out of 10 thought the interventions were useful and would recommend it to a fellow student. The “Tankevirus” smartphone app is freely available, and within 16 months, it was downloaded by 26.000 adolescents. Based on patient reported outcome measures, 7 out of 10 reported improvements in overall health and increased quality of life. The app includes several components to increase engagement with the intervention material, which is a necessary prerequisite for digital mental health interventions to be effective (26), and smartphone apps which have elements built in to promote engagement are associated with larger effect sizes (29). In this project we will include two different formats of the “Tankevirus”-interventions, in addition to a control condition:

- **“Tankevirus” therapist-guided group intervention:** The intervention will be delivered by therapists having extensive experience with this age group in the form of 3 weekly 75-minutes sessions to groups of approximately 30-35 participants. An online GDPR-compliant webinar-platform including chat-options will be used (edumeet.org). Adolescents will remain anonymous to each other to decrease barriers to participation. The adolescents will book their preferred timeslot online. For the participants randomized to this intervention, a certain waiting period (~1 week) must be expected. We will keep record of number of days waiting for each person and include this as covariate in the analysis.
- **“Tankevirus” smartphone app:** The app will be downloaded to their personal smartphone, and the app will give push-notifications once new modules are released – every day for 3 weeks. The app has several procedures built in for engagement purposes but will not involve contact with a therapist. Usage data will be recorded to verify compliance. The app is developed in accordance with the requirements of the Norwegian Health Authorities and complies with data protection laws.

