- **Assessment-only:** All assessments will be conducted, but no intervention will be provided to this group. The assessment only condition is necessary for investigating natural trajectory and form the baseline level for assessing risk reduction in the interventional groups.

Figure 1. Screenshot from GooglePlay of the “Tankevirus” smartphone app.

All interventions and assessments for all trial arms will be fully digitalized through a research app, which is essentially a modification to the already developed “Tankevirus”-app, including all preassessments and follow-ups. Human interaction is limited to the therapist-led group, otherwise automated nudges and notifications will remind the adolescents to complete assessments. This will be beneficial when considering the scalability and implementation of the intervention, should it be successful, and for evaluating whether human interaction indeed is a driver of the effect between interventions.

HYPOTHESIS: The main hypothesis is that the outcome related to the therapist-guided group intervention will be more effective in reducing number of relapses and time to relapse during the follow-up period when compared to the app-based approach, and that the app-based approach will be more efficacious compared to an assessment-only condition/care-as-usual (the control group).

PARTICIPANTS: Participants will primarily be recruited through large scale marketing campaign in social media (i.e., TikTok, Snapchat, Instagram) and web pages of user organizations, informing about this trial and the opportunity to take part. This is the most efficient way of reaching eligible participants, as clinicians seldom refer to such a trial ([name], PI of the StayFine-trial targeting adolescents in remission, *personal communication*, 21.07.24). Overall, 90 % of Norwegian adolescents are on social media (30). Currently, we have established contact with the social media coordinator in Mental Helse Ungdom. We will also post physical adds at places we expect adolescents to see them. Through other ongoing projects we have contact with ~150 general practitioners and we have established a collaboration with the low-threshold service UngArena.

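### The guided-versus-app contrast compares two delivery packages and cannot isolate the therapist's contribution, as sections 1.3 and 2.1 claim

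*Protocol*

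**What the plan says.** The protocol attributes the guided-versus-app contrast to the therapist in three places.

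- Section 2.1: "The head-to-head comparison of interventions will disentangle the level of clinician-involvement required".
- Section 1.3, end of the Interventions text: human contact occurs only in the therapist-led arm, and this is said to be useful "for evaluating whether human interaction indeed is a driver of the effect between interventions".
- Section 1.2: by assessing cost-effectiveness, "we can identify whether therapist involvement is necessary". The same section describes the arms as "two digital versions of a transdiagnostic prevention program with varying level of therapist guidance".

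The Interventions text in section 1.3 then describes the arms. The guided arm has "3 weekly 75-minutes sessions to groups of approximately 30-35 participants". On format: "An online GDPR-compliant webinar-platform including chat-options will be used". Participants book a timeslot, and "a certain waiting period (~1 week) must be expected"; days waited are recorded and used as a covariate. The other arm is an app on the participant's own phone, with new modules daily for three weeks: "The app has several procedures built in for engagement purposes but will not involve contact with a therapist". The third arm is assessment-only.

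The Hypothesis paragraph states superiority of guided over app. The Statistical power paragraph sizes time to relapse for a pairwise hazard ratio of 0.6 with 165 participants per group.

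**The concern.** A contrast between two arms can be credited to one component only if that component is what separates the arms. Here the presence of a therapist changes together with the format, the schedule of contacts and the expected start. If guided does better, the protocol's wording would credit human interaction, although a live group format or a different spacing of contacts could produce the same result. If the arms look alike, a therapist benefit and an opposing effect of another component could have cancelled out. How much clinician involvement is needed is a central question of the trial, so the published answer could go further than the design supports. The statistical analysis plan, which is not at hand, could not repair this: a component that never varies separately from the others cannot be separated by analysis.

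**Working it through.** The attribution rests on no stated figure, so there is nothing to reproduce for it. The check sets the arm descriptions side by side and then asks what one contrast can show.

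**1. What differs between the arms (section 1.3, Interventions)**

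| Feature | Guided | App |
|---|---|---|
| Therapist | Yes | No |
| Format | Live webinar with chat, groups of about 30–35 | Individual, on own smartphone |
| Contacts | 3 weekly sessions, 3 × 75 = 225 minutes | Daily modules for 3 weeks, about 7 × 3 = 21 releases |
| Wait | About 1 week expected | None described |
| Total time | 225 minutes | Not stated |

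At least three things change along with the therapist: format, number and spacing of contacts, and the expected wait. The direction and size of any difference in total dose are unknown. No arm offers the webinar without a therapist or the app with one.

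**2. The waiting-days covariate.** Follow-up runs from randomisation (section 1.3, Primary endpoint). The wait arises after randomisation and is described for one arm only. A variable that is about seven days in one arm and absent in the other carries nearly the same information as the arm indicator. Adjusting for it therefore cannot cleanly remove the timing difference. No adjustment is named for format or schedule.

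**3. Identification (illustration with assumed values).** Write HR(guided vs app) = HR(therapist) × HR(other components).

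- If 0.60 is observed and the other components contribute 1.0, 0.8 or 0.6, the therapist HR is 0.60/1.0 = 0.60, 0.60/0.8 = 0.75 or 0.60/0.6 = 1.00.
- If 1.0 is observed and the other components contribute 1.2 or 0.8, the therapist HR is 1/1.2 = 0.83 or 1/0.8 = 1.25.

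The data supply only the product, so every one of these splits fits equally well.

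**4. What a null result would show.** The relapse risk is not stated; 30% to 50% observed relapse per arm is assumed. With 165 per arm and a true HR of 1, SE(log HR) = √(2/(165 × risk)), and the 95% limits are exp(±1.96 × SE).

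| Assumed relapse | Events per arm | SE | 95% CI |
|---|---|---|---|
| 30% | 49.5 | 0.201 | 0.67–1.48 |
| 40% | 66.0 | 0.174 | 0.71–1.41 |
| 50% | 82.5 | 0.156 | 0.74–1.36 |

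Even with identical true effects, the interval would not exclude a relapse hazard 36% to 48% higher in one arm than in the other.

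As a cross-check, the Schoenfeld formula for HR 0.6 at two-sided 0.05 and 80% power gives 4 × (1.960 + 0.842)² / (ln 0.6)², which rounds up to 121 events. With 121 events, power is about 50% at HR 0.7 and 23% at HR 0.8. A moderate true advantage of the guided arm would often be missed.

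**The case against.** The strongest reply is that the confirmatory hypothesis is already a package comparison. It sets the guided group intervention against the app approach, and comparing deliverable formats is a legitimate pragmatic choice. Section 1.2 ties the need for a therapist to cost-effectiveness, which is a choice between packages. App versus assessment-only shows directly whether a therapist-free package works. All of this stands, and it is why the arms, endpoints and sample size need no change. It does not support the statements in sections 1.3 and 2.1 that the contrast evaluates human interaction or disentangles the clinician involvement required.

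A reader might also infer more than the documents support:

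- **That the app is self-paced, starts at once, or delivers a different total dose.** Pacing, immediate start and minutes per module are not stated.
- **That the guided arm lacks engagement features.** All arms run through a modified version of the app, with automated reminders to complete assessments. Which other features guided participants see is not described.
- **That peer support is an established rival explanation.** Group participants stay anonymous to each other, which weakens it.
- **That the wait is ignored.** A covariate is planned; the difficulty is that it nearly duplicates arm.
- **That the trial plans to read a null result as therapist redundancy.** Section 1.1 mentions a redundant therapist only conditionally, as background, and no decision rule says this.
- **That webinar attendance will go unrecorded.** The protocol is silent on it, which is missing operational detail and not an error.

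**Conclusion.** The point holds as one of attribution. The guided-versus-app contrast does not identify the effect of the therapist, because format, contact schedule and expected wait change with it and no arm varies the therapist alone. This follows from the protocol's own arm descriptions and needs no numerical assumption. The randomised comparison of the two packages, including their cost-effectiveness, remains valid; it would be wrong to conclude that the contrast is biased or uninformative.

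The interpretation of a null result is a linked, secondary matter. The hypothesis is one of superiority and the sizing is for a hazard ratio of 0.6, so a non-significant result would leave intervals between about 0.67–1.48 and 0.74–1.36. That range rests on 165 per arm, equal true effects and the assumed 30% to 50% relapse.

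**What to change.** 1. In section 1.3 (end of the Interventions text) and section 2.1, and in section 1.2 where cost-effectiveness is linked to the need for a therapist, restate the objective as a comparison of two delivery packages: a therapist-led webinar group and a self-guided app. Remove the claim that the comparison isolates human interaction or the clinician involvement required.
2. Add one sentence saying that a non-significant guided-versus-app result will not by itself be reported as showing that the therapist is unnecessary, and that the estimate will be presented with its confidence interval.

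This is rewording only. Arms, sample size, endpoints and analyses stay as they are. The cost is a less far-reaching claim.

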2.2. Measures for communication and exploitation

Open access publications in high-rank international journals will inform the scientific community. By reaching out to clinicians and policy makers with this newly derived knowledge about treatment efficacy and predictors of treatment success, we can implement this newly derived knowledge into clinical guidelines making appropriate recommendations. Also, reaching policy makers are central for securing funding to support the continued delivery of “Tankevirus”-courses and app.

The therapist-led part of “Tankevirus” would require building up competency in this specific method. Courses are already in place and supported by the Norwegian directorate of health. The digital online format of the intervention implies that each person being licenced, could deliver courses nationwide, supporting the scalability of the intervention. Infrastructure for referring remitted adolescents into these courses would need to be developed.

Should this trial be successful, it will allow the “Tankevirus”-program to be applied to a new target group. Since the app already is available and recommended as selfcare strategy for depression and anxiety within HelseNorge.no, the official website for information about and access to health services for Norwegian residents, our collaboration with user organizations will be essential in our efforts at reaching the adolescent who has the largest predicted effect from the app-version of “Tankevirus”. Presentations at national clinical conferences will be essential for transmitting knowledge to clinicians.

3. Implementation

ensure the quality of the trial and provide guidance on conducting decentralized trials. The persons with lived experience will ensure the quality of the participant information and make recommendation on how to recruit and retain participants, in addition to interpreting and disseminating the results. The project group cover expertise on all necessary areas, including clinical, theoretical, and methodological skills in clinical psychology, psychiatry, statistics, and project management, as well as lived experience and knowledge about the mental health care system.

3.2. Project organization and management

Project period: June 2025-June 2028.

Table 3: Gantt chart

Activity	Responsible	Year 1				Year 2				Year 3			
		Q1	Q2	Q3	Q4	Q1	Q2	Q3	Q4	Q1	Q2	Q3	Q4
Preparation													
Designing	RB, HB, KR, NIL, KBT												
Data protection	RB, KR												
Ethical approval	RB												
Preregistration	RB, NIL												
Piloting	RB, HB												
Recruiting patients	JRH, RB												
Data collection													
Interventions	BM, HB												
Follow-up	RB												
Statistical analysis													
Primary endpoint	RB, KR												
Exploratory analysis	RB												
Dissemination													
Publish inter.	NIL, RB, HB, KR												
Communication	RB, HB, JRH												

Through Nettskjema and Tjenester for sensitive data (TSD), the University of Oslo will provide research infrastructure for collecting informed consents digitally with MinID or BankID. This is the only identifiable information we will collect. The “Tankevirus” smartphone intervention is already developed and will be incorporated in a research platform allowing for all data to be collected in a streamlined, and anonymized manner. This app is currently being developed by Maths in Health and the anonymity of the platform will be assessed by SIKT for adherence to privacy regulations (GDPR).

References

1. World Health Organization. Mental Health of Adolescents 2021 [Available from: <https://www.who.int/news-room/fact-sheets/detail/adolescent-mental-health>].
